9.0 Procedures Involved*

9.1 Describe and explain the study design.

This project adheres to PCORI methodological standards. Patient-reported outcomes measured with validated and reliable instruments will be the basis for us to compare the effectiveness of two distinct evidence-based models for culturally competent diabetes health promotion through research with two diabetes self-management programs that each currently serve a large Latino patient population from low-income households in Albuquerque, New Mexico. Data will be gathered at baseline, and 3, 6, and 12 months by paid PDCSs (PDCSs) from the target patient population who will be members of the research team. *A priori*, we believe patient populations for each program will be similar, yet we will compare sample characteristics and assess treatment differences after adjusting for possible population differences including the use of propensity scores in our statistical models to mitigate self-selection bias, possible confounding, and heterogeneity of treatment effects. Trickett's conceptualization of "cultural situated-ness" discussed above provides the theoretical framework for this study.^{37,38} We follow National Institutes of Health (NIH) standards for mixed method research set by Creswell and colleagues³⁹ in our "embedded mixed method" research approach, integrating data from quantitative and qualitative components of the study in an iterative fashion.³⁹ Our quasi-experimental research design with pre-/post-testing will accommodate the fact that we are working with existing programs at two sites and that we will recruit patients who enter those programs during the study.⁴⁰ Our sample size (N=240) and power estimates are based on realistic evaluation of effect size. We provide a detailed project timeline with specific deliverables that include scientific and engagement milestones. We have assembled a research team with the expertise and experience in patient-engaged research necessary to conduct the proposed study and we have an institutional infrastructure that supports our academic and community partnerships.

9.2 Provide a description of all research procedures being performed and when they are performed, including procedures being performed to monitor subjects for safety or minimize risks.

Data Collection.

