Surveys. We will hire four individuals from the population of study to work as PDCSs. The PDCS at each site will administer a survey orally to all patient and social support participants at baseline (when they enter the study), with follow-up at 3, 6, and 12 months. The survey will consist of questions from or modified from four validated and reliable tools: 1.) The *Consumer Assessment of Healthcare Providers and Systems Cultural Competence Set (CAHPS-CC)*^{88,89} [as part of the programmatic assessment discussed in the preceding paragraph—will be administered at 3, 6 and 12 months only]; 2.) The *Diabetes Knowledge Questionnaire (DKQ)*^{51–53,112}; 3.) The *Patient Activation Measure (PAM-13)*^{55–62,113}; and 4.) The *Patient Health Questionnaire 9 (PHQ-9)*.^{70–73}

Interviews with patient and social support participants. We will conduct 72 interviews with patients and social supports (12/year x 2 sites x 3 years). Following Guest, Bunce and Johnson,¹¹² and [name]'s own experience with interview data, we believe that data sets of 12 interviews per site per year will capture a sufficient range of responses to achieve

PROTOCOL TITLE: Comparing Program Options for Latinos with Diabetes

thematic saturation. Our sampling frame for each set of 12 interviews will include six patients and six social supports. Interviews will be conducted with the social supports who correspond to the six patient interviewees. Interviews will follow the same format described in the programmatic assessment above. Spanish transcripts will be translated into English for analysis.

Focus groups. We will conduct 12 focus groups (2/year x 2 sites x 3 years). Focus group participants will be distinct from those recruited to participate in the interviews described in the preceding paragraph. Focus groups will include six distinct participants each (three patients and their corresponding social supports per focus group x 12 focus groups = 72 participants). The focus group questions and protocol will be an adaptation of that described above for the interviews.

Physical Measures. These measures will be obtained from patients at baseline with follow-up at 3, 6, and 12 months:

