11.0 Data Management* and Confidentiality

11.1 *Describe the data analysis plan, including any statistical procedures.*

Descriptive statistics will be calculated to summarize patient characteristics. Means and standard deviations or medians and quartiles will be calculated for continuous variables and will be compared across site by ANOVA or Kruskal-Wallis test, depending on the distribution of the data. Frequencies and percentages will be calculated for categorical variables and will be compared with the chi-square test or Fisher's exact test, as appropriate. Significant differences will be noted and to adjust for possible confounding, those variables will be considered for inclusion as covariates in the analyses for the primary and secondary outcomes in addition to other clinically meaningful variables and their interactions. We expect patient characteristics to be similar across the two treatment sites; however, to control for potential differences in the populations, we will adjust for potential confounding covariates by using propensity scores to stratify subjects into groups based on the probability that they attended a particular treatment site given particular demographic characteristics including sex, age, primary language, level of education, nativity, and type of insurance. Patients will be grouped by quintile of propensity score for a total of five strata and each will be analyzed for the primary and secondary outcomes independently. Analyses will be performed in standard statistical software such as SAS 9.4, R 3.1, and/or Stata 14. Propensity score matching allows for causal inference in our non-experimental settings by selecting similar subsets of comparison units between treatment groups across a high-dimensional set of pretreatment characteristics.

We will complement our quantitative analyses by conducting a rigorous, disciplined, empirical analysis of data from key staff/provider interviews (Aim #1), patient/social support interviews and focus groups (Aims #1 & 2), and Patient Advisory Board interview transcripts.

PROTOCOL TITLE: Comparing Program Options for Latinos with Diabetes

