Hypothesized Effect Size for Intervention on Main Patient-Centered Outcome. We hypothesize that the CCM model, because following Trickett it is more effectively *situated* with patient culture and socio-economic context,^{37,38} will be superior to the DSMS in its ability to increase diabetes knowledge and patient activation, lower A1c, and improve depression scale scores and BMI among participants. Using the CCM model, One Hope has had many patients improve their health, including individuals who have been able to reduce or stop taking their diabetes medication. One Hope staff note that people participating in the diabetes program have changed their food- and physical activity-related behaviors and attitudes. Lowered blood sugar levels and improved diabetes self-maintenance have been reported anecdotally. One Hope conducted a preliminary analysis of patient medical records and found that CCM diabetes patients demonstrated statistically significant decreases in A1c values at months #5, 8, 11, 14, 18 and 22 after they joined One Hope's program.¹⁰²

The quantitative Primary Outcome for this study is improved patient capacity for diabetes self-management:

1.) Diabetes knowledge will be measured using the *DKQ summed score*. Hypothesis: The CCM model will result in a larger increase in DKQ summed scores from baseline to 6 months with a Cohen's f effect size (ES) = 0.09 as compared to the DSMS. Previously published studies evaluating culturally competent diabetes management programs report meaningful changes in DKQ summed scores with effect sizes of 0.03 to 0.16 in studies ranging in sample sizes per arm from 10 to 189.^{51,53,54,103}

2.) Patient activation will be measured using the *PAM-13 raw score*. Hypothesis: The CCM model will result in a larger increase in PAM-13 raw scores from baseline to 6 months with Cohen's f ES = 0.07 as compared to the DSMS. Previously published studies evaluating culturally competent diabetes management programs report changes in PAM-13 raw scores with meaningful effect sizes of 0.01 to 0.16 in studies ranging in sample size per arm from 26 to 133 (per Shah, Co-I [name], and colleagues¹⁰⁴).^{66,105-107}

The quantitative Secondary Outcome for this study is successful diabetes self-management as measured by improvement in A1c, BMI, and PHQ-9. Self-management will be measured through change in A1c, BMI, and depression index (PHQ-9).

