- 1.) Hypothesis: The CCM model will result in a larger decrease in percent A1c from baseline to 6 months with Cohen's f ES = 0.06 as compared to the DSMS. Previously published studies and institutional experience evaluating culturally competent diabetes management programs report changes in percent A1c with effect sizes of 0.01 to 0.06 in studies ranging in sample size per arm from 26 to 133.^{66,105-107}
- 2.) Hypothesis: The CCM model will result in a larger decrease in BMI from baseline to 6 months than DSMS with a clinically meaningful difference of 1.5 kg/m² between the groups (Cohen's f ES = 0.06).^{67,68}
- 3.) Hypothesis: Compared to DSMS, CCM will result in a larger decrease (by 3 points) in PHQ-9 scores from baseline to 6 months (Cohen's f ES = 0.06).¹⁰⁷⁻¹⁰⁹

Note: It is coincidental that the effect sizes (and power) are the same for each of the three secondary outcomes

Power Calculations. We will recruit N=240 patient-social support pairs (n=120 per site) with anticipated 20% attrition to obtain complete data on at least n=96 per site. Comparing response changes on the DKQ, PAM-13, and DHQ-9 from baseline to 6 months between the CCM to the DSMS, the two-sided Type I error rate was adjusted for the number of comparisons made (four comparisons for the co-primary outcomes) using a Bonferroni correction ($\alpha=0.0125$). The power analyses for detecting site differences among change scores were based on multiple linear regression models including demographic characteristics, participants' perceived cultural competence of providers (CAHPS-CC), and social supports' change scores on the DHQ, PAM-13, and DHQ-9 as covariates. We report Cohen's f effect sizes based on the regression method.^{110,111}

The power for the primary endpoints with n=96 per site and $\alpha=0.025$ are as follows:

- 1.) Change in DKQ summed score: $\Delta_{CCM-DSCS} = 2.2$ (SD = 3.8), power = 96%, Cohen's f effect size (ES) = 0.09
- 2.) Change in PAM-13 raw score: $\Delta_{CCM-DSCS} = 12.7$ (SD = 24.8), power = 85%, Cohen's f ES = 0.07

The power for the secondary endpoints with n=96 per site and $\alpha=0.017$ for comparing the CCM to the DSMS:

- 1.) Change in A1c: $\Delta_{CCM-DSCS} = -0.5$ (SD = 1.0), power = 84%, Cohen's f ES=0.06.
- 2.) Change in BMI: $\Delta_{CCM-DSCS} = -1.5$ (SD = 3), power = 84%, Cohen's f ES=0.06.
- 3.) Change in depression scores (PHQ-9): $\Delta_{CCM-DSCS} = -3$ (SD = 6), power = 84% Cohen's f ES = 0.06.

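### The only regression described for the co-primary DKQ and PAM-13 change scores omits the patient's own baseline score, and no Aim 2 analysis model fills the gap

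*Combined protocol and SAP*

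**What the plan says.** The design is not randomised. Section 9.1 states: "Our quasi-experimental research design with pre-/post-testing will accommodate the fact that we are working with existing programs at two sites". Section 11.2 defines the co-primary outcomes as a "larger increase in DKQ summed scores from baseline to 6 months" and a "larger increase in PAM-13 raw scores from baseline to 6 months", each comparing the CCM site with the DSMS site.

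Section 11.1 has a modelling paragraph for Aim 3 (A1c, with BMI and depression handled similarly) but no counterpart for Aim 2, to which the co-primary outcomes belong. The only regression described for DKQ and PAM-13 is the basis of the power calculation in 11.2. There, the analyses for "detecting site differences among change scores were based on multiple linear regression models including demographic characteristics", perceived provider cultural competence on the CAHPS-CC, and the supports' "change scores on the DHQ, PAM-13, and DHQ-9 as covariates". (I read DHQ and DHQ-9 as slips for DKQ and PHQ-9.)

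The propensity score in 11.1 uses "particular demographic characteristics including sex, age, primary language, level of education, nativity, and type of insurance". Section 11.1 also says that characteristics differing significantly by site, and other clinically meaningful variables, will be considered as covariates for the primary and secondary outcomes. Baseline DKQ and PAM-13 are not named.

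Both scores are available: under 9.2 the data collectors "administer a survey orally to all patient and social support participants at baseline" and again at 3, 6 and 12 months, and the survey includes both instruments.

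**The concern.** A baseline score usually carries information about the later change, because people who start low tend to gain and people who start high tend to fall back. Leaving it out has two possible consequences.

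The first is precision. If baseline predicts change, its contribution stays in the residual and widens the interval for the site effect.

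The second is confounding. If the sites differ on baseline score, the change-score contrast can mix the programme effect with the different starting points. Nothing else listed clearly guards against this. The CAHPS-CC is not given at baseline, and the supports' change scores also arise after entry, so demographics are the only pre-entry variables in the described model and the only ones named for the propensity score.

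At stake is the headline comparison of the two programmes. A choice that can alter the estimate is left open until after the data are seen.

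**Working it through.** **Inputs from section 11.2.** 96 patients per site with complete data; two-sided tests; DKQ difference 2.2, SD 3.8, stated power 96%; PAM-13 difference 12.7, SD 24.8, stated power 85%. Two alphas are printed for the co-primary outcomes: 0.0125 in the Bonferroni sentence and 0.025 above the power list.

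**Assumed, because the documents do not say.** Baseline to 6-month correlation rho from 0.3 to 0.7; equal variances at both times; stated SDs are raw change SDs.

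**Step 1: the plan's own figures.** Power = Φ(δ / (SD × √(2/n)) − z), with z = 2.241 at alpha 0.025 and 2.498 at alpha 0.0125; √(2/96) = 0.1443.

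- DKQ: 2.2 / (3.8 × 0.1443) = 4.011. At 0.025, Φ(1.770) = 96.2%. This matches the stated 96%.
- PAM-13: 12.7 / (24.8 × 0.1443) = 3.548. At 0.025, Φ(1.307) = 90.4%, which does not match 85%. At 0.0125, Φ(1.050) = 85.3% (84.6% with the noncentral t), which does.

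The two stated powers therefore fit different alphas. That is a separate matter, but it is why both alphas appear below.

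**Step 2: precision.** With outcome variance σ², the variance of change is 2σ²(1 − rho). After adjusting for baseline it is σ²(1 − rho²). The ratio is (1 + rho)/2, so the residual SD is SD × √((1 + rho)/2).

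| rho | Variance ratio | DKQ SD | DKQ power, 0.025 | PAM-13 SD | PAM-13 power, 0.025 | PAM-13 power, 0.0125 |
|---|---|---|---|---|---|---|
| no adjustment | 1 | 3.80 | 96.2% | 24.80 | 90.4% | 85.3% |
| 0.3 | 0.65 | 3.06 | 99.7% | 19.99 | 98.5% | 97.1% |
| 0.5 | 0.75 | 3.29 | 99.2% | 21.48 | 96.8% | 94.5% |
| 0.7 | 0.85 | 3.50 | 98.3% | 22.86 | 94.6% | 91.2% |

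A baseline gap of d SD between sites inflates the adjusted variance by about 1 + d²/4: 1% at 0.2 SD and 6% at 0.5 SD. The net gain survives over this range of rho.

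**Step 3: bias if scores regress to a common mean.** The unadjusted contrast is shifted by (1 − rho) × gap, against the site that starts higher. The outcome SD is SD of change / √(2(1 − rho)). For an assumed gap of 0.2 SD:

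- rho 0.3: DKQ 0.7 × 0.2 × 3.21 = 0.45 points (20% of 2.2); PAM-13 0.7 × 0.2 × 20.96 = 2.93 points (23% of 12.7).
- rho 0.7: DKQ 0.3 × 0.2 × 4.91 = 0.29 points (13%); PAM-13 0.3 × 0.2 × 32.02 = 1.92 points (15%).

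**Step 4: does adjustment always cure this?** Simulation with 96 per site, 1,500 replicates, rho 0.5, no true site effect, baseline gap 0.5 SD; mean estimate in SD units:

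| How the sites differ | Change score | Baseline-adjusted |
|---|---|---|
| Scores regress to a common mean | −0.245 | 0.001 |
| Sites have stable, different means | 0.005 | 0.255 |

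With no gap, both estimates are within simulation error of zero.

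**The case against.** A reader might infer that the plan commits itself to a biased primary analysis, and that adding the baseline score would remove the bias. The documents support neither.

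- The covariate list is the basis of a power calculation, not a declared analysis model, and 11.1 leaves a route by which other clinically meaningful variables could enter. That stands, so omission from the final analysis is not settled. But the route is discretionary and does not name the baseline scores. If the 11.2 regression is not the analysis model, the co-primary outcomes have no stated model.
- With non-randomised sites, change-score and baseline-adjusted analyses rest on different untestable assumptions (Lord's paradox). Step 4 shows each failing where the other succeeds. Stable site differences are plausible, since section 3.1 describes different entry routes: programme registration at one site; clinic calls, exit interviews and flyers at the other. Error in the measured baseline score would also leave some confounding. This stands in full.
- Nothing shows that baseline DKQ or PAM-13 will differ. The protocol expects similar populations and applies common eligibility criteria, although it also plans for self-selection. The 0.2 SD gap is only an illustration.
- No correlation is given, so baseline cannot be called the strongest predictor of change. If the stated SDs are already residual to the listed covariates, the gain may be smaller than tabulated.
- Recomputed power without the covariate is already about 85% or higher for PAM-13 and 96% for DKQ at 0.025. The gain is useful for PAM-13 and slight for DKQ.

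**Conclusion.** The point holds as a gap in specification with a measurable cost in precision. The one regression described for the co-primary change scores omits a covariate collected at baseline, the propensity score does not supply it, and no Aim 2 model settles the matter.

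Under equal variances, rho 0.3 to 0.7 and raw change SDs, adjustment would add about 6 to 12 points of power for PAM-13 at alpha 0.0125, about 4 to 8 points at alpha 0.025, and about 2 to 3.5 points for DKQ at alpha 0.025.

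On bias, the supportable statement is conditional. If sites differ at entry and scores regress to a common mean, the unadjusted contrast shifts by (1 − rho) times the gap. If site means are stably different, the change score is the unbiased analysis. Because the two can disagree, the primary one should be named before the data are examined. Baseline adjustment is the natural choice here because 11.1 already relies on conditioning on pretreatment characteristics.

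**What to change.** In 11.1, add an Aim 2 paragraph, and align 11.2 with it:

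- The primary model for each co-primary outcome is the 6-month score (or, equivalently for the site effect, the change) on site, adjusted for the patient's own baseline score on that instrument and the pre-specified baseline covariates or propensity stratum.
- Baseline DKQ and PAM-13 are added to the propensity score variables.
- The change score without baseline adjustment is a named sensitivity analysis, with a sentence on the assumption behind each analysis.
- Section 11.2 states whether the quoted SDs are raw or residual, and which baseline to 6-month correlation is assumed.

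The cost is SAP wording and one extra covariate per model; no new data are needed. The downside is that the two analyses may disagree, and the report would then have to discuss why.
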